7.7.2. Response/Progression Categories

The following definitions for disease response and progression will be used according to the following MRI and clinical criteria:

Complete Response (CR): Requires **all** of the following:

1. Disappearance of all enhancing measurable and non-measurable disease sustained for at least 4 weeks. In the absence of a confirming scan at least 4 weeks later, this scan will be considered only stable disease.
2. No new lesions
3. Stable or improved non-enhancing (T2/FLAIR) lesions
4. Patients must be off corticosteroids (or on physiologic replacement doses only).
5. Stable or improved clinical assessments

Partial Response (PR): Requires **all** of the following:

1. $\geq 50\%$ decrease in sum of products of perpendicular diameters of all measurable enhancing lesions compared with baseline, sustained for at least 4 weeks. In the absence of a confirming scan at least 4 weeks later, this scan will be considered only stable disease.
2. No progression of non-measurable disease
3. No new lesions
4. Stable or improved non-enhancing (T2/FLAIR) lesions
5. Steroid dose should be the same or lower compared with baseline scan.
6. Stable or improved clinical assessments.

Progressive Disease (PD) is defined by *any* of the following:

1. $\geq 25\%$ increase in sum of products of perpendicular diameters of enhancing lesions compared with the smallest tumor measurement [obtained either at baseline (if no decrease) or best response], on stable or increasing doses of corticosteroids.
2. Any new enhancing measurable lesion
3. Clear clinical deterioration not attributable to other causes apart from tumor (e.g. seizures, medication adverse effects, therapy complications, stroke, infection) or attributable to changes in steroid dose. The definition of clinical deterioration is left to the discretion of the investigator.
4. Clear progression of non-measurable disease
5. Failure to return for evaluation as a result of death or deteriorating condition.

Stable Disease (SD): Requires **all** of the following:

1. Does not qualify for CR, PR, or PD as defined above.
2. Stable non-enhancing (T2/FLAIR) lesions on same or lower dose of corticosteroids compared with baseline scan
3. Clinically stable

The response and progression criteria to be used in this study are summarized in **Table 13**:

Table 13. Summary of the RANO response Criteria:

Criterion	CR	PR	SD	PD
T1w CE	None	≥ 50 % ↓	<50%↓ but <25 %↑	≥25% ↑*
T2w/FLAIR	Stable or ↓	Stable or ↓	Stable or ↓	↑
New lesions	None	None	None	Present *
Corticosteroids	None	Stable or ↓	Stable or ↓	NA†
Clinical status	Stable or ↑	Stable or ↑	Stable or ↑	↓*
Response requirement	All	All	All	Any *

The arrows indicate the direction of measured change from last exam. Abbreviations: RANO: Response Assessment in Neuro-Oncology, CR: complete response, PR: partial response, SD: stable disease, PD: progressive disease, T1w: T1 weighted. T2w: T2 weighted, CE: contrast enhancement, FLAIR: fluid-attenuated inversion recovery, NA: not applicable. * Progression occurs when this criterion is present.

Of note, patients who require increased corticosteroids within 2 weeks of MRI assessment (relative to the dose taken at the time of the prior assessment) cannot be classified as CR, PR, or SD and should be classified as non-evaluable at that time point. Conversely, patients who decrease corticosteroids within 2 weeks of MRI assessment (relative to the dose taken at the time of the prior assessment) cannot be classified as PD and should be classified as non-evaluable.

Unscheduled Assessments:

If an unscheduled assessment was performed and the subject has not progressed, every attempt should be made to perform the subsequent assessments at their scheduled visits (relative to the date of first study drug infusion).

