7.7 Efficacy Evaluations

7.7.1. Anti-Tumor Effect Definitions

Modified Response Assessment in Neuro-Oncology (RANO) criteria ([Ellingson et al, Neurotherapeutics 2017](#)) will be used to assess for tumor response and progression, with definitions as outlined below. Radiologic response will be assessed by comparing the pretreatment baseline and on-treatment MRI scans. Radiologic progression will be determined by using the smallest tumor measurement at either the pretreatment baseline or after initiation of study medication. MRI scans will be performed no less frequently than every 8 weeks. The MRI scan should be performed within 7 days prior to a cycle start (and ideally within 3 days prior). Adjustments to this 7 day window are allowable per the treating physician's discretion; however restaging scans MUST BE performed and reviewed before the subsequent cycle's dose may be initiated. MRIs will be interpreted by the attending neuro-radiologist at the University of Pennsylvania assigned as a sub-investigator on this study.

Measurable disease should be defined as contrast enhancing lesions with a minimum size of *both* perpendicular measurements greater than or equal to 10mm. For example, if the largest diameter is 15 mm but the perpendicular diameter is 8 mm, this would constitute *non-measurable disease*. Up to a total of five target measurable lesions should be defined and ranked from largest to smallest. Non-measurable disease should be defined as lesions that are too small to be measured (less than 1 cm in both perpendicular dimensions), lesions that lack contrast enhancement (non-enhancing disease), or lesions that contain a poorly defined margin that cannot be measured or segmented with confidence.

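### Table 13's footnote measures change from the last exam, which contradicts the baseline and smallest-measurement references set in 7.7.1 and 7.7.2

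*Combined protocol and SAP*

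**What the plan says.** Section 7.7.1 sets two reference scans. For response: "Radiologic response will be assessed by comparing the pretreatment baseline and on-treatment MRI scans". For progression: "Radiologic progression will be determined by using the smallest tumor measurement at either the pretreatment baseline or after initiation of study medication".

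The numbered definitions in 7.7.2 repeat both. PR needs a 50% or greater "decrease in sum of products of perpendicular diameters of all measurable enhancing lesions compared with baseline, sustained for at least 4 weeks". PD needs a 25% or greater increase "compared with the smallest tumor measurement [obtained either at baseline (if no decrease) or best response], on stable or increasing doses of corticosteroids". The steroid condition for PR also uses baseline: "Steroid dose should be the same or lower compared with baseline scan". SD uses the baseline scan for steroids too, and requires that none of CR, PR or PD is met.

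Section 7.7.2 then introduces Table 13: "The response and progression criteria to be used in this study are summarized in" that table. The table carries the same 50% and 25% thresholds, but its footnote reads: "The arrows indicate the direction of measured change from last exam". Nothing in the document says whether the text or the table governs, or limits the footnote to certain rows.

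The PD column of Table 13 also shows an increase in T2/FLAIR without the asterisk that the footnote uses to mark a criterion of progression.

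**The concern.** The same thresholds are tied to different reference scans in the text and in its summary. At the first on-treatment scan the last exam is the baseline, so the two agree. From the second on-treatment scan they can part.

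Three outcomes are exposed:

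- **ORR, the primary endpoint.** Section 8.1 makes it binary (CR or PR versus neither), and 8.2.1 tests it in 16 evaluable Cohort A subjects.
- **PFS.** Section 2.2.2 dates progression by the same criteria.
- **Steroid eligibility for PR and SD.** Section 5.8.3 expects SRS to cause edema and 5.6 allows corticosteroids at any dose for it, so a dose above baseline on study is plausible.

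Section 7.7.1 assigns reading to a site neuro-radiologist who is a sub-investigator. No independent review is described that would catch a reading taken from the table.

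**Working it through.** **1. The plan's own design figure.** Inputs from 8.2.1: null 5%, alternative 25%, one-sided 0.05, N = 16, power 80%. The document does not state the cut-off, so it is derived here. With X the number of responders, P(X ≥ 3) = 1 − Σ(k=0..2) C(16,k) p^k (1−p)^(16−k).

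- p = 0.05: 1 − (0.4401 + 0.3706 + 0.1463) = 0.043.
- p = 0.25: 1 − (0.0100 + 0.0535 + 0.1336) = 0.803.
- A cut-off of 2 would give 0.189 at p = 0.05, which is too high.

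The stated 80% is reproduced with success at 3 or more of 16. One subject is 1/16 = 6.25 points of ORR, and 2/16 versus 3/16 separates failure from success.

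**2. Text and footnote applied to the same scans.** The sums of products below are illustrative and are not trial data.

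| Sequence | Against last exam | Against the reference in 7.7.1–7.7.2 |
|---|---|---|
| 100, 70, 49 | 70/100 and 49/70 = 0.70: −30% each time, PR threshold not met | 49/100 = 0.49: −51% from baseline, PR threshold met |
| 40 (smallest so far), 49, 60 | 49/40 = 1.225 and 60/49 = 1.224: about +22% each time, PD threshold not met | 60/40 = 1.50: +50% from the smallest measurement, PD threshold met |

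In the first row, a scan at 49 or lower at least 4 weeks later confirms PR under the text, provided the other PR items hold. In the second row, PD is put off by at least one scan interval. Section 7.7.1 sets that interval at 8 weeks or less.

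**3. Steroid row.** This row gives direction only; PR and SD allow a stable or falling dose. Take a subject whose dose rises between baseline and the first on-treatment scan and is then unchanged at the second. Against the last exam the dose is stable and PR is open. Against baseline it is higher, and 7.7.2 does not allow PR. The note under Table 13 on steroid changes within 2 weeks of an MRI compares with the prior assessment, so it would not catch this at the second scan.

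**4. Sensitivity of the primary test.** The misclassification rates here are assumptions, because the document gives none. Success is 3 or more of 16.

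- True ORR 25%, with 10%, 20% or 30% of responders missed: effective rates 0.25 × 0.9 = 0.225, 0.25 × 0.8 = 0.20 and 0.25 × 0.7 = 0.175. Power is 0.733, 0.648 or 0.549.
- Null rate raised from 5% to 6%, 7% or 8% by wrongly accepted responses: type I error is 0.067, 0.097 or 0.131.

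**5. Why SD needs its own wording.** Take 100, 40, 60. The last scan is −40% from baseline, which fits the SD cell, and +50% from the smallest measurement, which is PD. A footnote that set SD against baseline alone would put one scan in two columns. The text avoids this because SD excludes anything that meets PD.

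**6. T2/FLAIR under PD.** PD item 4 in 7.7.2 covers clear progression of non-measurable disease, and 7.7.1 counts non-enhancing lesions as non-measurable. The text therefore reaches T2/FLAIR progression. In the table, the last row says any PD criterion suffices, while the missing asterisk suggests that this one does not trigger progression.

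**The case against.** The strongest reply is that the operative rule is already clear. Sections 7.7.1 and 7.7.2 name the reference scans explicitly, Table 13 is only a summary, and its footnote explains arrows without giving a denominator for the percentages. Read as a threshold rule, the footnote defeats itself: 1000, 450, 440 is −55% and then −2% from the last exam, so a stable PR might never be confirmed. A specialist reader is unlikely to apply that against the numbered definitions. Most of this stands, and it limits the risk. It does not clear the steroid row, where direction is the whole criterion and the footnote supplies the wrong comparison.

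A reader might infer more than the document supports, in three ways:

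- **That shrinkage after an enlargement becomes a PR.** In 100, 140, 69 the last scan is −51% from the last exam and −31% from baseline. A single scan is not a PR under either reading: 7.7.2 requires the decrease to be sustained for at least 4 weeks and otherwise counts the scan as stable disease.
- **That the text omits T2/FLAIR from PD.** It does not use the term in the PD list, but item 4 covers it through the definition in 7.7.1.
- **That the primary result will be wrong.** Any single reclassified subject can move 3/16 to 2/16 in a trial of this size. That shows sensitivity, and does not show that an error will occur.

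**Conclusion.** The footnote is wrong as written and should be corrected. It contradicts the reference scans in 7.7.1 and 7.7.2 for tumor response, for progression, and for the steroid dose under PR and SD. A reader who works from the table could, from the second on-treatment scan, miss a gradual response, call PD late, or accept a PR on a steroid dose above baseline.

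The possible effect is 6.25 points of ORR per subject, with the derived success boundary at 3 of 16. How often it would happen cannot be estimated from the document. The power and type I error figures rest on assumed rates and show only how sensitive the test is. A reader who follows the numbered definitions would classify correctly, and the 4-week confirmation rule limits false responses. The T2/FLAIR mismatch is secondary, and it depends on the printed table lacking the asterisk.

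**What to change.** Delete the reference to the last exam from the Table 13 footnote. State instead that the reference scans are those in 7.7.1 and 7.7.2:

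- tumor change for CR and PR is measured from the pretreatment baseline;
- tumor change for PD is measured from the smallest prior measurement, baseline included;
- SD means that none of CR, PR or PD is met;
- the steroid dose for PR and SD is compared with the baseline scan.

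Leave the separate 2-week steroid note with its own reference to the prior assessment.

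Reconcile the T2/FLAIR entry in the PD column with PD item 4 and do not remove it. Removal would take the table further from the text.

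The cost is one footnote and one table cell, best settled before further images are read. N = 16, the derived cut-off, the alpha of 0.043 and the power of 0.803 stay as they are.

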7.7.3. Study continuation beyond initial progressive disease

Immunotherapeutic agents including PD-1 inhibitors such as INCMGA00012 may produce antitumor effects by potentiating endogenous cancer-specific immune response, which may manifest as initial worsening of enhancement on MRI (i.e., pseudoprogression). In addition, the response patterns seen with immunotherapeutics may extend beyond the typical time course of responses seen with cytotoxic agents, and can manifest a clinical response after an initial increase in tumor burden or even the appearance of new lesions. For these reasons, the immune-related response criteria (irRC) have endorsed continuation of study therapy beyond radiographic evidence of progression for clinically stable patients undergoing immune based therapies (Seymour et al, [Lancet Oncol 2017](#)).

Therefore, the following adaptations of the RANO criteria, as reflected in the recently published Immunologic Response Assessment in Neuro-Oncology (iRANO) criteria ([Okada et al, Lancet Oncol 2015](#)), will be used to assess tumor progression for patients treated on this study:

- Potential Pseudoprogression: If radiologic imaging *within the first 6 months* from the first dose of immunotherapy shows confirmed PD by mRANO criteria, as defined in the above section, participants not experiencing significant clinical decline

may be allowed to continue study treatment for up to 3 months from the time of the scan showing confirmed PD. Patients who have radiographic evidence of further progression after 3 months, or who decline significantly any time, will be classified as progressive disease with the date of disease progression back-dated to the first date the participant met criteria for PD and such participants will be discontinued from study therapy. In participants who have initial evidence of radiographic PD, it is at the discretion of the treating physician whether to continue a participant on study treatment for up to 3 months pending confirmation of PD on follow-up imaging. This clinical judgment decision should be based on the participant's overall clinical condition, including performance status, clinical symptoms, and laboratory data. Subjects may receive study treatment while waiting for confirmation of PD if they are not experiencing significant clinical decline and if:

- the subject is believed to demonstrate clinical benefit from the study regimen as determined by the treating physician;
- the subject is adequately tolerating study therapy

Subjects who have been on the study drugs for *more than 6 months* must come off study for disease progression at the first time that radiologic criteria for confirmed PD are met.

7.7.4. MRI Procedures

MRI of the brain is performed once every 8 weeks on study as per standard of care for the management of recurrent GBM. The MRIs performed for this study do not include experimental sequences or coils or any experimental contrast. These MRIs do require the use of an FDA-approved gadolinium-based contrast agent. The gadolinium will be used in accordance with the FDA label for gadolinium-based contrast.

IV Line Placement – This is required to administer the contrast agent. Multiple needlesticks may be necessary if a vein cannot be properly accessed and this will be carried out with the subjects' permission.

IV Contrast Risks- As mention above, part of the MRI study will require the injection of a gadolinium contrast agent into the blood stream. There is a rare possibility that the subject could have an adverse reaction to the contrast agent such as rash, hives, itching, mild headache and nausea. The subject may also experience some minor discomfort and low risk of bleeding, infection and bruising associated with Intravenous catheter placement. Recently, FDA has also required a new class warning for all gadolinium-based contrast agents (GBCAs) for MRI concerning gadolinium remaining in patients' bodies, including the brain, for months to years after receiving these drugs. The long-term risks of this retention are not well elucidated; Gadolinium retention has not been directly linked to adverse health effects in patients with normal kidney function, and the FDA has concluded that the benefit of all approved GBCAs continues to outweigh any potential risks. Also, there is a possible risk of nephrogenic systemic fibrosis (NSF, also

referred to as nephrogenic fibrosing dermopathy or NFD) occurring following administration of a GBCA in subjects with known moderate to severe renal disease (with a glomerular filtration rate or GFR < 30 mL/min/1.73m²). However, such patients are not eligible for this trial (see [Section 4; Eligibility Criteria](#)). In addition, serial creatinine values will be checked for each subject once monthly throughout the course of the trial. If at any point a subject's GFR falls below 30 mL/min/1.73m² or a rise in creatinine above baseline suggests an acute kidney injury, that subject must undergo a repeat serum creatinine test within 24 hours prior to the next planned MRI scan with contrast. This MRI with contrast should not be performed until the GFR is above 30 mL/min/1.73m² and is stable improving on two additional tests each separated by 48 hours.

Pregnancy Clause - Although there are no known risks related to MRI on pregnant women or a fetus, there is a possibility of yet undiscovered pregnancy related risks. Since there is potential danger to the fetus from participating in this protocol for a pregnant woman, we will exclude pregnant women. A negative urine or serum pregnancy test will be required before a woman of child-bearing potential can participate in this study. If the subject is post-menopausal for at least one year or has undergone a hysterectomy, the subject will not be required to undergo a pregnancy test prior to enrolling in this study and undergoing MRI scans. Gadolinium-based IV contrast agents are not approved in pregnant women (pregnant women will be excluded from this trial).

Metallic Foreign Fragments/Flying Object Clause -The known risks associated with this study are minimal. Implanted medical devices and metallic foreign fragments inside the body may pose a risk if you were to enter the MRI magnet room. Therefore, questions regarding medical and work history will be asked prior to the exam. The greatest risk is a magnetic object flying through the air toward the magnet and hitting the subject. To reduce this risk, we require that all people involved with the study remove all magnetic metal from their clothing and all magnetic metal objects from their pockets. No magnetic metal objects are allowed to be brought into the magnet room at any time except by approved personnel. In addition, once subject is in the magnet, the door to the room will be closed so that no one inadvertently walks into the room.

Magnetic Fields Health Risks Statement--There is no known health risk associated with exposure to magnetic fields during an MRI. There are minimal risks from the loud noise associated with the MRI scanner and from the discomfort of lying on a hard surface. We shall provide the subject with protective earplugs as necessary and make every attempt to ensure comfort with blankets, etc. during time in the scanner.

7.8 Safety Assessments

Subjects are evaluated for safety according to the office visit and laboratory evaluation schedule outlined in [Table 8](#) and [Table 9](#) ([Section 6](#)). Safety and AE definitions, recording, and reporting are outlined in detail in [Section 9](#).

7.9 Tissue/Blood collection for correlative analyses, PK, and ADA

For all subjects in this study (both Cohort A and Cohort B), informed consent will be obtained to collect a formalin-fixed, paraffin-embedded (FFPE) preserved component of tumor tissue from the subject's initial surgical tumor resection for exploratory correlative analyses. This surgery

will have already been performed prior to their enrollment on this protocol as part of standard of care therapy for glioblastoma.

For subject in the surgical arm only (Cohort B, N=16), both fresh frozen and FFPE preserved components of tumor tissue will also be collected from the surgery that subjects will undergo as part of this protocol (i.e., the subject's surgery for recurrent GBM).

In addition, in both Cohorts A and B 60 mL of peripheral blood will also be collected for future exploratory correlative analyses. These 60 mL blood samples will be collected at the time points outlined in the SOE (**Table 8** and **Table 9**).

All subjects will be asked to consent to collection of an FFPE preserved component of tumor tissue from any surgical brain tumor resection or brain tumor biopsy that is performed (as clinically indicated) after the subject has discontinued the study treatment. If a subject comes off study for progressive disease, initiates another treatment regimen per standard of care, and then has another tumor resection, collection of FFPE preserved tissue will not occur.

The exploratory endpoints of this study are outlined in [Section 2](#). All correlative analyses will be performed in University of Pennsylvania laboratories with the following exceptions: pharmacokinetic (PK) and anti-drug antibody (ADA) measurements will be performed by Syneos Health, and GITR expression by IHC will be performed by Mosaic Laboratories. In addition to the correlative assays listed in [Section 2](#), other assays relevant to understanding mechanisms or predictors of clinical benefit and/or resistance to INCMGA00012 and INCAGN01876 in GBM may be performed on these tissue and blood samples in the future based upon emerging data and future hypotheses. The informed consent form reflects this flexibility for future research use of subject biospecimens collected during the course of this study.

No results of tissue or blood correlatives will be recorded in the subject's electronic medical record and will not be used in any way to guide treatment or clinical decision making.

